5.2.7.3 Electrocardiographic Data

A list of subjects with abnormal 12-lead ECG parameters at screening will be presented. Baseline ECG parameters (heart rate, cardiac rhythm, PR interval, QRS interval, QT interval, and QT interval corrected for heart rate) will be summarized for the final visit/early termination visit time point. For exploratory purposes, analyses of QT, QT interval corrected for heart rate using Fridericia's formula, and QT interval corrected for heart rate using Bazett's formula will be completed using accepted definitions for outliers (eg, frequency counts of interval changes from baselines \geq 30 msec and \geq 60 msec) as well as analyses of central tendency of active drug versus placebo and active dose versus placebo.

Confidential Page 74 of 95

5.2.7.4 Laboratory Data

Mean changes from baseline at each post-baseline time point for each laboratory variable will be presented. In addition, each reading will be classified as below, within, or above the normal range, based on ranges supplied by the laboratory used. Shift tables for the baseline and follow-up measurements will be presented and clinically significant changes will be summarized.

Potentially clinically significant ranges will be defined in the SAP for selected parameters, and the number and percent of subjects meeting these criteria summarized. Tabular summaries will include only those subjects in whom the values represent a treatment-emergent worsening.

Listings of laboratory parameters will be presented. Listings will flag results above and below the normal range as well as those that meet criteria for being potentially clinically significant (whether or not a treatment-emergent worsening). Separate listings for each hematology, chemistry, and urinalysis parameter will show results that meet criteria for being potentially clinically significant. In addition, for subjects who have one or more results that meet criteria, all laboratory results will be displayed.

5.2.7.5 Vital Signs

Summary statistics for the absolute vital sign value and the changes from baseline will be presented by treatment group for each visit.

The number and percentage of subjects reporting potentially clinically meaningful observations will be summarized:

- Systolic BP: supine $\leq 80 \text{ mmHg or } \geq 140 \text{ mmHg}$
- Diastolic BP: supine $\leq 40 \text{ mmHg or } \geq 90 \text{ mmHg}$
- Pulse rate: supine ≤ 50 bpm or ≥ 100 bpm
- Respiration rate: < 8 or > 20 breaths per minute

In addition, shift tables from baseline to each post-baseline visit in relation to the clinically meaningful ranges specified above will be presented for each of these vital sign parameters.

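### The vital-sign outlier count ignores each subject's baseline, and no planned table counts individuals with a marked rise or fall at any visit

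*Combined protocol and SAP*

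**What the plan says.** Section 5.2.7.5 plans three displays of vital signs.

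- **Means:** "Summary statistics for the absolute vital sign value and the changes from baseline will be presented by treatment group for each visit".
- **Outlier count:** "The number and percentage of subjects reporting potentially clinically meaningful observations will be summarized". The limits are absolute: systolic ≤80 or ≥140 mmHg and diastolic ≤40 or ≥90 mmHg, both supine; "Pulse rate: supine ≤ 50 bpm or ≥ 100 bpm"; and "Respiration rate: < 8 or > 20 breaths per minute". No condition on baseline or on size of change is attached. I read the count as subjects with at least one such reading, since no visit is named.
- **Shift tables:** "shift tables from baseline to each post-baseline visit in relation to the clinically meaningful ranges specified above will be presented".

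The two preceding sections treat outliers differently. For laboratory values beyond potentially clinically significant ranges, section 5.2.7.4 says: "Tabular summaries will include only those subjects in whom the values represent a treatment-emergent worsening". Section 5.2.7.3 gives counts of QT interval changes from baseline of at least 30 and 60 msec as its example of an outlier definition. The synopsis defines the vital-sign safety endpoint as a change from baseline.

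Section 3.5.5.2 makes supine blood pressure and pulse optional; the sitting readings carry no such label.

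**The concern.** Subjects are 55 to 85 years old and no entry criterion sets a blood-pressure limit, so some will plausibly be at or above 140 mmHg before the first dose. They enter the count whatever the drug does. At the other end the blood-pressure limits are extreme. A systolic fall from 135 to 100 mmHg is a large change for one person, yet it crosses no limit and appears in the shift table as normal to normal.

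A reader who goes to the outlier count for individual blood-pressure changes may therefore find a large background on the high side and almost nothing on the low side. Similar percentages in the two arms would say little about marked individual rises or falls.

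**Working it through.** **No figure to reproduce.** The protocol states no baseline distribution and no expected outlier rate, so the sizes below rest on assumptions.

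**Inputs from the protocol.** The limits in 5.2.7.5; six on-treatment clinic visits with vital signs (weeks 13, 26, 39, 52, 65 and 78, Table 7); 80 subjects per arm (section 3.1).

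**Assumed inputs.** Systolic mean μ 125–140, SD σ 15–18; diastolic mean 72–80, SD 9–11; pulse mean 65–70, SD 9–11; within-subject correlation ρ 0.5–0.7; normal readings; no drug effect; all six readings present in the position named.

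**Step 1: high at baseline.** P = 1 − Φ((140 − μ)/σ). With μ = 125 and σ = 15 this is 1 − Φ(1.00) = 0.16; with μ = 140 it is 0.50.

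**Step 2: flagged at least once in six visits.** With subject effect b ~ N(0, ρσ²), P = 1 − E[Φ((140 − μ − b)/(σ√(1 − ρ)))⁶], and similarly for the other limits. Simulation of 400,000 subjects per scenario gives:

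| Limit | Ever flagged | Expected per 80 | Of those flagged, beyond the limit at baseline |
|---|---|---|---|
| Systolic ≥140 | 37–86% | 29–69 | 29–62% |
| Diastolic ≥90 | 8–49% | 6–39 | 13–40% |
| Systolic ≤80 | 0.02–3.0% | 0.01–2.4 | not computed |
| Diastolic ≤40 | 0–0.9% | 0–0.75 | not computed |
| Pulse ≤50 | 5–29% | 4–23 | not computed |

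For systolic ≥140, the last column passes one half only when the assumed mean is about 135 or higher. Counting only subjects below 140 at baseline who later reach it, the no-effect rate is 23–40%. That is a smaller background, but still a background.

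**Step 3: what different counts would pick up.** No test is planned, so power is only a yardstick. Assume systolic mean 128–138, total SD 17, within-person visit SD 8–11, 80 per arm and two-sided 5%, with power ≈ Φ(|p₁ − p₀|/√(p₁(1 − p₁)/80 + p₀(1 − p₀)/80) − 1.96):

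| Uniform shift | Count | Power |
|---|---|---|
| +5 mmHg | ≥140, as written | 0.30–0.40 |
| +5 mmHg | ≥140 and baseline below 140 | 0.16–0.36 |
| +5 mmHg | ≥140 and a rise of ≥20 | 0.51–0.63 |
| −8 mmHg | ≤80, as written | 0.08–0.20 |
| −8 mmHg | a fall of ≥20 | 0.87–0.98 |

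Under the −8 mmHg shift, only about 1–6% of subjects with a fall of at least 20 mmHg are also flagged at ≤80.

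**Step 4: the planned mean-change summary on the same yardstick.** SD of change = √2 × 8 = 11.3 to √2 × 11 = 15.6. SE of the arm difference = SD × √(2/80) = 1.79 to 2.46. Power at one visit is Φ(8/SE − 1.96) = 0.99 to 0.90 for −8 mmHg, and Φ(5/SE − 1.96) = 0.80 to 0.53 for +5 mmHg.

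**Step 5: background of a change count.** With no drug effect, a fall of at least 20 mmHg at one visit has probability Φ(−20/11.3) = 0.04 to Φ(−20/15.6) = 0.10, and more over six visits. Such a count must be read against placebo.

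**The case against.** The case on the other side is substantial, and much of it stands.

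- **Baseline is not ignored in the section as a whole.** The shift tables separate subjects already beyond a limit from new cases at each visit, and changes from baseline are summarized by arm. This stands. What remains is the lack of an any-visit count, and changes inside the limits.
- **Mean changes detect a uniform shift at least about as well.** Step 4 bears this out. They do not show how many individuals changed markedly, so a large change in a minority can be hidden in the average.
- **Adverse-event reporting also captures individuals.** Section 4.1.1 has clinically significant vital-sign findings recorded as adverse events, and 5.2.7.2 counts pre-existing conditions that worsen after the first dose. A reader might infer that the outlier count is the only any-time look at individuals; it is not. The adverse-event route does depend on investigator judgement and not on a tabulated rule.
- **The remedy goes beyond the laboratory rule.** Section 5.2.7.4 gives no minimum change, so any cut-off is a new choice. This is correct. Step 3 shows why one is useful: requiring only a normal baseline does no better than the present count for a +5 mmHg shift.
- **Details may still come.** Section 5.2 defers to a SAP finalized before database lock. That makes the addition easy to place there.

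**Conclusion.** The point holds as a minor improvement. The count in 5.2.7.5 has no baseline reference, unlike its laboratory and QT neighbours, and no planned table gives an any-visit count of individuals with a marked rise or fall. On the assumed distributions, a large share of both arms is flagged at systolic ≥140 without any drug effect, and about 0–3% reach the low blood-pressure limits.

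Three stronger readings are tempting and are not supported:

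- **That the high limit mostly flags pre-existing hypertension.** The protocol has no figure for this. The share already high at baseline is 29–62% for systolic and 13–40% for diastolic on assumed inputs, and one reading of ≥140 is not a diagnosis.
- **That the low limits are almost never reached.** This fits blood pressure only; pulse ≤50 could be reached by 5–29%.
- **That the arm comparison is biased.** Allocation is 1:1 and randomized, so the background is similar in both arms. It dilutes a difference and does not create one.

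The power figures compare displays under uniform shifts with complete readings. They do not describe a planned test. If supine readings are often missing, the count as written rests on fewer subjects than assumed here.

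**What to change.** Keep the current table and add to 5.2.7.5 or the SAP, by arm and for each vital sign:

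- **(a)** an any-visit treatment-emergent count: a post-baseline value beyond the limit and worse than baseline by a prespecified amount;
- **(b)** any-visit counts of rises and, separately, of falls of a prespecified size, whatever the absolute limit.

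Use as denominator the subjects with a baseline and at least one post-baseline reading. Fix the change amounts before unblinding; 20 mmHg systolic, 10 mmHg diastolic and 15 bpm are examples only.

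Reconcile 5.2.7.5, which states the blood-pressure and pulse limits for supine readings, with 3.5.5.2, which makes those readings optional, so that the counts use the position actually recorded.

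The cost is SAP wording and one extra table from readings already scheduled. The downside is that the cut-offs are a matter of choice and the new counts carry some background of their own (step 5).

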3.5.2.1 Screening Phase (Day -42 to -7)

The assessments during the screening phase (screening, screening 2, screening 3/baseline MRI) will determine the subjects' eligibility to enter the study and comply with the protocol requirements. Subjects must meet all the criteria during all the screening visits in order to be enrolled in the study.

The following procedures will be performed and recorded during screening phase:

Screening visit 1 (clinic visit)

- Informed consent
- Demographic information and medical history
- Eligibility criteria
- Blood sample for serum chemistry, complete blood count (CBC), thyroid panel, and liver function tests
- Electrocardiogram (ECG)
- Physical and neurological exams, and HIS score assessment
- Vital signs and body weight
- Urine sample for urinalysis and urine drug screen (amphetamines, benzodiazepines, cannabinoids, opiates, methadone, and alcohol)
- ISLT, MMSE, GDS, practice BPS-O, CDR score (participant and study partner), Columbia Suicide Severity Rating Scale (C-SSRS), and HIS assessments
- AEs/SAEs and prior medication reporting

Screening visit 2 (imaging visit)

- An amyloid-imaging PET scan with Neuroceq (florbetaben), Amyvid (florbetapir), or Vizamyl (flutemetamol) will be performed unless there is documented evidence of an amyloid-positive scan, and it will only be conducted on prospective participants who meet all the other eligibility criteria (see Appendix 8.2).
- AEs/SAEs and prior medication reporting

Screening visit 3/baseline MRI (imaging visit)

Baseline visit will occur on day -1 within 12 days ± 2 days of the S3/B MRI visit.
 S3/B MRI will occur up to 2 weeks prior to Baseline; the Tau scan needs to occur 1 or more days before the cognitive visit. This MRI is to be conducted prior to the cognitive Baseline visit; up to 2 weeks can occur between S3/B and cognitive Baseline visit.

Confidential Page 52 of 95

- A 3T MRI imaging scan will occur and will only be conducted on prospective participants who meet all the other eligibility criteria (see Appendix 8.3).
 - 3T MRI (structural: magnetization-prepared gradient echo [MP-RAGE] or radiofrequency-spoiled gradient echo [IR-SPGR], fluid attenuation inversion recovery [FLAIR] sequence, T2) (previous MRI scans will not be allowed).
- A 3T task activated fMRI scan will occur during the same MRI session after completing the structural MRI sequences. An in-scanner version of the BPS-O will be used as the fMRI task (*optional procedure at JHU only*).

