3.5.5.2 Vital Signs and Body Weight

Vital signs will include body temperature (F or C), respiratory rate, supine (optional) and sitting radial pulse rates, and supine (optional) and sitting systolic and diastolic blood pressures (BPs). Supine recordings, if possible, will be made after the subject has been recumbent for 3 minutes. Body weight without shoes will be recorded in pounds or kilograms whenever vital signs are recorded.

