4.1 Definitions and Criteria

4.1.1 Adverse Events

Per International Conference on Harmonisation (ICH) E2A: An AE is any untoward medical occurrence in a subject or clinical investigation subject administered a pharmaceutical product and which does not necessarily have to have a causal relationship with this treatment. An AE can therefore be any unfavorable and unintended sign (including an abnormal laboratory finding, for example), symptom, or disease temporally associated with the use of a medicinal product, whether or not considered related to the medicinal product.

Events meeting the definition of an AE **include**:

- Exacerbation of a chronic or intermittent pre-existing condition including either an increase in frequency and/or intensity of the condition
- New conditions detected or diagnosed after investigational product administration even though it may have been present prior to the start of the study
- Signs, symptoms, or the clinical sequelae of a suspected drug interaction
- Signs, symptoms, or the clinical sequelae of a suspected overdose of either investigational product or a concomitant medication

Clinically significant abnormal findings (laboratory test results, vital signs, physical examination findings, ECGs, radiologic exams, or other studies) should be recorded as AEs. A "clinically significant" finding is one that affects clinical management, including additional visits, monitoring or referrals, diagnostic tests or alteration of treatment, or that is considered clinically significant by the investigator. A clinically significant finding may be a change in a test that has previously been abnormal but now requires additional action.

When a medical or surgical procedure is performed, the condition that leads to the procedure should be recorded as the AE.

Events that **do not** meet the definition of an AE include:

• Anticipated day-to-day fluctuations or expected progression of pre-existing disease(s) or condition(s) present or detected at the start of the study unless

Confidential Page 61 of 95

judged by an investigator to be more severe than expected for the subject's underlying condition

- Abnormal laboratory, ECG, or vital sign measurements that are not labelled clinically significant (see definition above)
- Situations where an untoward medical occurrence did not occur (social and/or convenience admission to a hospital)
- Pregnancy
- Overdose in the absence of other AEs will not be reported as an AE in its own right

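### The blood pressure and pulse limits and their shift tables use supine readings only, but supine readings are optional, so sitting-only readings go unflagged

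*Combined protocol and SAP*

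**What the plan says.** Section 3.5.5.2 describes what is measured: "supine (optional) and sitting radial pulse rates, and supine (optional) and sitting systolic and diastolic blood pressures (BPs". It adds: "Supine recordings, if possible, will be made after the subject has been recumbent for 3 minutes". Supine pressure and pulse are therefore optional twice over, and sitting is the only posture without that label.

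Section 5.2.7.5 describes the analysis in three parts.

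- **Summary statistics.** "Summary statistics for the absolute vital sign value and the changes from baseline will be presented by treatment group for each visit". No posture is named.
- **Counts against fixed limits.** Numbers and percentages of subjects beyond set limits. Systolic pressure (≤ 80 or ≥ 140 mmHg), diastolic pressure (≤ 40 or ≥ 90 mmHg) and pulse are each specified as supine; the pulse entry reads "Pulse rate: supine ≤ 50 bpm or ≥ 100 bpm". Respiration rate (< 8 or > 20 per minute) carries no posture.
- **Shift tables.** "shift tables from baseline to each post-baseline visit in relation to the clinically meaningful ranges specified above will be presented". These reuse the limits of the second part.

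No section gives a limit for sitting values, or says what to do when a visit has a sitting reading only.

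**The concern.** The analysis depends on a measurement that sites may skip, and does not use the one they are asked to take. Two planned safety displays could be thinner than they look, by an amount the reader of the tables would not see.

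What is at stake follows from Section 4.1.1. A clinically significant finding there is "one that affects clinical management, including additional visits, monitoring or referrals, diagnostic tests or alteration of treatment", or one the investigator considers significant, and it is recorded as an adverse event. The events that are not adverse events include "Abnormal laboratory, ECG, or vital sign measurements that are not labelled clinically significant (see definition above". For readings in that second group, the fixed-limit counts and the shift tables are the planned displays that flag individual values without relying on investigator judgement. A group mean can hide a few outlying readings.

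**Working it through.** There is no figure in the plan to reproduce. The check is a comparison of text, followed by an illustration.

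**Step 1: posture collected against posture analysed**

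| Measure | Collected (3.5.5.2) | Limit and shift table (5.2.7.5) |
|---|---|---|
| Systolic pressure | Sitting; supine optional | Supine only |
| Diastolic pressure | Sitting; supine optional | Supine only |
| Pulse | Sitting; supine optional | Supine only |
| Respiration rate | No posture | No posture |

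The first three rows conflict; the fourth does not.

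**Step 2: consequence for the counts.** A supine limit cannot be applied without a supine reading, so an out-of-range sitting value at a sitting-only visit is not flagged. The display counts subjects rather than visits, so the same subject is still counted if a supine reading at another visit is out of range. The denominator is not stated. A subject with no supine reading might be left out, or might be counted as within limits, which would understate the percentage.

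**Step 3: consequence for the shift tables.** A shift needs a classified value at baseline and at the later visit. A sitting-only later visit has no entry for pressure or pulse. A subject with no supine reading at baseline has no such shift at any visit.

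**Step 4: illustration of size.** Let p be the share of visits with a supine reading. The documents give no value, so every p below is assumed. Assume also that the supine value would be out of range whenever the sitting value is.

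- Subject out of range at k visits, supine recording independent between visits: chance of being counted = 1 − (1 − p)^k.
- Share of shift pairs usable at a given visit: p² if recording is independent between visits; p if it is a fixed habit of the site or subject.
- The last two columns multiply that share by 80, the planned number per arm (Section 3.1), assuming full attendance.

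| p (assumed) | Counted, k = 1 | Counted, k = 2 | Usable pairs per arm, independent (80p²) | Usable pairs per arm, fixed habit (80p) |
|---|---|---|---|---|
| 0.95 | 95% | 99.75% | 72.2 | 76 |
| 0.80 | 80% | 96% | 51.2 | 64 |
| 0.50 | 50% | 75% | 20 | 40 |
| 0.20 | 20% | 36% | 3.2 | 16 |

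Worked row, p = 0.50: 1 − 0.50² = 0.75; 80 × 0.50² = 20; 80 × 0.50 = 40. Under a fixed habit, the chance of being counted stays at p however many visits are out of range.

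The range is wide because p is unknown. The table shows how the loss behaves; it does not estimate it.

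**The case against.** **The SAP can settle this.** Section 5.2 provides for a detailed SAP, signed before database lock and unblinding, in which departures from the described analyses are to be recorded. That stands as a route to the fix. It does not remove the point: the combined document contains no SAP text on vital signs that changes the posture. Section 5.2.7.5 also states its limits outright, whereas Section 5.2.7.4 leaves the laboratory ranges to the SAP.

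**The effect is modest.** This also stands. Only descriptive displays are involved; no hypothesis test, efficacy analysis or sample size depends on them.

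**Stronger readings that the documents do not support.**

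- A reader might infer a biased comparison between arms. The trial is double-blind and randomised 1:1 in blocks at each site, and nothing suggests that supine recording would differ by arm. With a denominator of subjects who have a supine reading, the likely result is fewer evaluable readings.
- A reader might infer that sitting readings are complete. Section 3.5.5.2 only leaves sitting unmarked as optional. Visits can be missed or held remotely (Sections 5.2.1 and 5.2.2), and the week 78 follow-up after early termination may be by telephone (Table 7).
- A reader might infer that the vital-sign baseline is in doubt, because Section 3.5.2.1 lists "Vital signs and body weight" at screening as well. Table 7 has a visit named Baseline, on day −1, with vital signs. That is the ordinary reading, and confirming it is routine detail for the table shells.

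**Conclusion.** The mismatch is real and plain on the text: the pressure and pulse limits, and the shift tables that use them, rest on an optional supine reading, with no sitting limit and no fallback. Followed as written, the plan leaves sitting-only readings unflagged and keeps those visits out of the pressure and pulse shift tables.

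The size cannot be determined. It is negligible if supine readings are nearly always taken and substantial if they seldom are; the documents do not say which, and the illustrative figures do not support a claim either way.

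Nor does the text support reading this as a loss of vital-sign safety reporting in general. The synopsis endpoint of change from baseline is served by the by-visit summaries, and clinically significant findings still reach the adverse event tables. Severity is minor. Confidence is high about the wording, and low about how much it matters in practice.

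**What to change.** Before database lock and unblinding, reconcile Sections 3.5.5.2 and 5.2.7.5, in the SAP that Section 5.2 provides for or by amendment, in one of two ways:

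- base the pressure and pulse counts and shift tables on the sitting posture, the one not marked optional; or
- keep supine, and state that the sitting value is used when no supine value exists, with both readings of a shift pair in the same posture.

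Under either choice the sponsor decides which limits apply to sitting values, since the documents give limits for supine values only; none is proposed here. Each table should show the number of subjects with an evaluable reading (for shifts, with both readings), so that any thinning is visible.

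The cost is a change of wording and table shells, plus the sponsor's confirmation of limits for sitting values. No new data are needed. Deciding before unblinding also avoids choosing the posture with treatment codes known.
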